As this is an observational study, the results of [¹⁸F]FLT PET/CT are not used to direct therapy. The duration of therapy is determined on the basis of clinical grounds by the referring physician, and is not influenced by the FLT study.

6.iii.6.e. Duration of Follow Up:

Patients will be followed until the time of their treatment failure or they are otherwise lost to follow-up, at which time they are considered off study. This is typically 5 years or less but may be as great as 7 years. Patients lost to follow-up will be tracked for overall survival to every extent possible based on information from public databases.

6.iii.7. EXPECTED TOXICITIES AND DOSING DELAYS / DOSE MODIFICATIONS

Not applicable to an observational imaging trial.

6.iii.8. ADVERSE EVENTS REPORTING

Qualifying Adverse Events (AEs), including Serious Adverse Events (SAEs), as defined herein, will be reported via the FDA Adverse Event Expedited Reporting System (AERS). For this IND we will report adverse events based on the FDA final rule for IND safety reporting requirements under 21 CFR part 312 published on September 29, 2010 and implemented on March 28, 2011. This investigational study is not a BA or BE study so 21 CFR part 320 is not applicable. Adverse events will also be reported to the local IRB according to their requirements.

6.iii.8.a. General Definitions (from 21 CFR 312.32 (a))

Adverse Event (AE): An **Adverse Event** is an untoward medical occurrence associated with the use of the drug in humans, whether or not considered drug related. For this study the drug is [¹⁸F]FLT and adverse events would include any events experienced by a study participant **during the Adverse Event reporting period defined in Table 6.iii.4 Study Calendar** whether or not it was considered to be related to the [¹⁸F]FLT.

Adverse Reaction: An **Adverse Reaction** is any adverse event caused by a drug. In this study the drug is [¹⁸F]FLT.

Suspected adverse reaction means any adverse event for which there is a reasonable possibility that the drug caused the adverse event. For the purposes of IND safety reporting, "reasonable possibility" means there is evidence to suggest a causal relationship between the drug and the adverse event. A suspected adverse reaction implies a lesser degree of certainty about causality than adverse reaction, which means any adverse event caused by a drug.

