An **adverse event or suspected adverse reaction** is considered "**unexpected**" if it is not listed in the investigator brochure or is not listed at the specificity or severity that has been observed; or, if an investigator brochure is not required or available, is not consistent with the risk information described in the general investigational plan or elsewhere in the current application.

An **adverse event or suspected adverse reaction is considered "serious"** if, in the view of either the investigator or sponsor, it results in any of the following outcomes: Death, a life-threatening adverse event, inpatient hospitalization or prolongation of existing hospitalization, a persistent or significant incapacity or substantial disruption of the ability to conduct normal life functions, or a congenital anomaly/birth defect. Important medical events that may not result in death, be life threatening, or require hospitalization may be considered serious when, based upon appropriate medical judgment, they may jeopardize the patient or subject and may require medical or surgical intervention to prevent one of the outcomes listed in this definition. Examples of such medical events

include allergic bronchospasm requiring intensive treatment in an emergency room or at home, blood dyscrasias or convulsions that do not result in inpatient hospitalization, or the development of drug dependency or drug abuse.

An **adverse event or suspected adverse reaction is considered “life-threatening”** if, in the view of either the investigator or sponsor, its occurrence places the patient or subject at immediate risk of death. It does not include an adverse event or suspected adverse reaction that, had it occurred in a more severe form, might have caused death.

Investigational Agent: An investigational agent is any agent held under an Investigational New Drug (IND) application. For purposes of this study, 3'-deoxy-3'-[¹⁸F]-fluorothymidine ([¹⁸F]FLT) is the investigational agent.

6.iii.8.b. AE Reporting Requirements

The investigators on this protocol will report any suspected adverse events that occur after [¹⁸F]FLT administration and within the specified follow-up period to the sponsor, [name], and they will work together to determine whether there was an adverse event or adverse reaction and the severity of the adverse event or reaction.

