Attribution of cause: The physician investigators will determine whether an adverse event was related to a medical treatment or procedure. Definitions taken from our work with CTEP and NIH give the following definitions for "Attribution" that we will adopt for this IND study: Attribution is a clinical determination, by the investigator, as to whether an AE is related to a medical treatment or procedure. Attribution categories are:

- **Definite:** The AE is **clearly related** to a treatment or procedure
- **Probable:** The AE is **likely related** to a treatment or procedure
- **Possible:** The AE **may be related** to a treatment or procedure
- **Unlikely:** The AE is **likely unrelated** to a treatment or procedure
- **Unrelated:** The AE is **clearly not related** to a treatment or procedure

NOTE: Attribution is part of the assessment of an adverse event. Determining that an event is 'unlikely related' or 'unrelated' to a study agent or procedure does NOT make the event unreportable, or disqualify the event as an AE. As defined above, an AE is reportable as specified herein if it occurred: "**during the Adverse Event reporting period defined in the protocol**, or by applicable guidance, regulation, or policy."

6.iii.8.f. Adverse Event Reporting

Expedited AE reporting for this study will be done through the Cancer Consortium IRB and FDA and as required by FDA MedWatch. These requirements are briefly outlined in the table below.

Table 6.iii.2 Reporting Requirements

	Unexpected		Expected
	Adverse Reaction (known or suspected attributable to the use of [¹⁸ F]FLT)	AE not attributable to [¹⁸ F]FLT	AE, AR
	Serious including life-threatening (or death)	Nonserious	Life-Threatening or serious or not serious
Reporting Time Requirement to the FDA	Report to FDA ASAP and within 7 days of discovery of event (section 6.iii.8.7)	Annual Continuation Review submission	Annual Continuation Review submission
Reporting Form for the FDA	IND Safety report of potentially serious risk	Annual Reports / Case reports	Not applicable to [¹⁸ F]FLT
Reporting Time Requirement to the local IRB	Report to IRB ASAP within 10 days of discovery of event (suspected is defined as 50% probability attributable to [¹⁸ F]FLT study) this also includes any increased risks with the study even without an AE	At continuation review time	At continuation review time

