Reporting form for the IRB	Expedited Reporting Form for Unanticipated Problems or Noncompliance and Adverse Event Reporting Form	Form for Unanticipated Problems or Noncompliance, Case reports on continuation form, Data Safety Monitoring Reports	Form for Unanticipated Problems or Noncompliance, Case reports on continuation form, Data Safety Monitoring Reports

6.iii.8.g. Expedited Adverse Reaction Reporting Guidelines

Life-threatening (or fatal) adverse reactions must be reported within 7 days to the FDA. The FDA should be notified as soon as the adverse reaction is discovered by telephone or fax or email. The instructions and forms are available at <http://www.fda.gov/Safety/MedWatch/HowToReport/default.htm>. The report should be sent ASAP by mail and followed with a follow-up report. Individual IND safety reports to FDA are submitted on the Medwatch FDA Form 3500A as an "IND Safety Report". The form should be sent to The Director, Office of Generic Drugs in the Center for Drug Evaluation and Research at FDA. The address and phone numbers are available at: <http://www.fda.gov/AboutFDA/CentersOffices/CDER/ucm119100.htm>.

All life threatening adverse reactions reports are submitted to the FDA, our local IRB and to all investigators. A copy of the report is kept on file.

6.iii.8.h. Protocol-Specific Expedited Adverse Event Reporting Exclusion

Not applicable for this IND agent

6.iii.8.i. Routine Adverse Event Reporting

Routine Adverse Event Reporting will be done to both the FDA and local IRB as detailed in the table 6.iii.2 .

6.iii.9. PHARMACEUTICAL INFORMATION

6.iii.9.a. Production of the Radiopharmaceutical

3'-Deoxy-3'-[¹⁸F]fluorothymidine (FLT): will be produced at the University of Washington according to the methods described in Section 7 of this IND (Chemistry, Manufacturing and Controls).

6.iii.9.b. Reported Adverse Events and Potential Risks

A list of the adverse events and potential risks associated with [¹⁸F]FLT are provided in Section 6.iii.8.

6.iii.9.c. Agent Accountability

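### Section 6.iii.8.g names an FDA addressee that nothing else in the plan supports, and its expedited-reporting sentences are narrower than Table 6.iii.2; the two need to be reconciled

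*Combined protocol and SAP*

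**What the plan says.** Section 6.iii.8 places safety reporting under the IND rules of 21 CFR part 312 and adds: "This investigational study is not a BA or BE study so 21 CFR part 320 is not applicable". It says that qualifying adverse events "will be reported via the FDA Adverse Event Expedited Reporting System (AERS"). Section 6.iii.8.a says "An investigational agent is any agent held under an Investigational New Drug (IND) application" and identifies FLT as that agent.

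Table 6.iii.2, in section 6.iii.8.f, has a column for unexpected reactions known or suspected to be due to FLT. Its expedited entry is headed "Serious including life-threatening (or death"). The FDA timing is "Report to FDA ASAP and within 7 days of discovery of event (section 6.iii.8.7"), and the IRB timing is within 10 days.

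Section 6.iii.8.g, the expedited-reporting guideline, says "Life-threatening (or fatal) adverse reactions must be reported within 7 days to the FDA". It puts individual IND safety reports on Form 3500A and then gives the addressee: "The form should be sent to The Director, Office of Generic Drugs in the Center for Drug Evaluation and Research at FDA". On distribution it says: "All life threatening adverse reactions reports are submitted to the FDA, our local IRB and to all investigators".

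**The concern.** Staff would open section 6.iii.8.g after a serious reaction, so its wording is operative. Two things in it do not fit the rest of the plan.

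The first is the addressee. The plan describes an investigational agent under an IND, and nowhere describes FLT as a generic product or links the generics office to this IND. The addressee sentence follows directly on the sentence about individual IND safety reports in general, so it governs all of them and not only the life-threatening ones.

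The second is scope. Section 6.iii.8.a separates serious from life-threatening, and gives bronchospasm treated intensively in an emergency room as an example of a serious event. Section 6.iii.8.d describes an allergic reaction to the injection as ranging from serious to life-threatening, so the reaction the plan itself anticipates can fall on either side of the line. Section 6.iii.8.e adds that no events are expected and all will count as unexpected, so no serious FLT reaction leaves the expedited column by being expected. At stake is whether such a report reaches the right desk on the right clock.

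**Working it through.** This is a check of text against text. The plan gives no figure to reproduce, and the only arithmetic is the exposure count. The column assignments in Table 6.iii.2 are read from the order of its entries.

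**Addressee.** Sections 6.iii.8 and 6.iii.8.a give the IND basis, part 312 and the not-BA/BE statement. Section 6.iii.8.g gives the Office of Generic Drugs. No section says which FDA office or division holds the IND. The addressee is therefore unsupported by the documents, but they cannot show it to be wrong.

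**Scope and clock for an unexpected reaction attributed to FLT.**

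| Reaction | Table 6.iii.2 | Section 6.iii.8.g |
|---|---|---|
| Life-threatening or fatal | FDA 7 days, IRB 10 days | FDA 7 days; reports of life-threatening reactions go to FDA, IRB and all investigators, with no IRB clock |
| Serious, neither life-threatening nor fatal | FDA 7 days, IRB 10 days | Form 3500A applies as an IND safety report; no clock and no distribution stated |

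The texts agree on the FDA clock in the first row. In the second row the table sets clocks and 6.iii.8.g is silent. The distribution sentence also does not name fatal reactions, although the 7-day sentence does.

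**Links between the texts.** Section 6.iii.8.e refers the reader to Table 6.iii.1 for reporting, but that is the enrollment table; the reporting table is 6.iii.2. The table refers to section 6.iii.8.7, which does not exist in the current lettering. Counting a, b, c, d, e, f, g, the seventh subsection is g, so g is the likely target, by inference. Both pointers a reader would follow are faulty.

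**Channel.** Section 6.iii.8 names AERS. Section 6.iii.8.g has notice by telephone, fax or email, followed by a mailed report on Form 3500A. The plan does not say how these relate.

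**Exposure.** Section 6.iii.4.d allows up to 40 patients, plans three to four scans each, and expects 25% to have only one or two.

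- Ceiling: 40 × 4 = 160 injections.
- Patients with one or two scans: 0.25 × 40 = 10, leaving 30 with three or four.
- Low end: 30 × 3 + 10 × 1 = 100.
- High end: 30 × 4 + 10 × 2 = 140.

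These count injections, not reports. Section 6.iii.8.c states that no adverse events have been reported with FLT to date.

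**The case against.** The strongest reply is that nothing is lost. Table 6.iii.2 is in force and sends every serious FLT-attributable reaction to the FDA and the IRB with a deadline. Section 6.iii.8.g does not exclude those reactions, and its form sentence covers IND safety reports in general. Section 6.iii.8.c promises all investigators any information on reported FLT events. For life-threatening or fatal reactions, 6.iii.8.g also calls for immediate notice to the FDA by telephone, fax or email, so the mailed form is not the only contact. AERS is a system and Form 3500A is a form, and the plan does not show them to be incompatible.

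Most of this stands, and it rules out three stronger readings that a reader might infer:

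- *Serious reactions that are not life-threatening go unexpedited.* The table expressly expedites them.
- *Reports are being sent to the wrong office.* The documents name no office as holder of the IND, so this cannot be shown from them.
- *Expedited reporting is the only early warning.* The plan also has monitoring during infusion (6.iii.6.a), a next-day call after each scan (6.iii.6.b.3), investigator reports to the sponsor (6.iii.8.b) and prompt sponsor review (6.iii.8.e).

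The reply does not remove the mismatch itself. Section 6.iii.8.f describes the table as only a brief outline, and the cross-references that should join the table to the procedure are both faulty. The promise in 6.iii.8.c carries no deadline.

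**Conclusion.** The point holds as an inconsistency in an operative safety-reporting instruction. The addressee for all individual IND safety reports has no support elsewhere in the plan and needs to be confirmed. Section 6.iii.8.g and Table 6.iii.2 differ on which reactions the stated 7-day FDA clock covers, and 6.iii.8.g limits its distribution sentence to life-threatening reactions. The consequence is a possible misaddressed form, or confusion for someone working from 6.iii.8.g alone.

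The exposure range assumes full enrollment of 40 and the scan completion expected in section 6.iii.4.d. The number of reports affected cannot be estimated from the documents and may be very small. Sample size, power and analysis do not depend on this point. It should be corrected because the text concerns patient safety and the correction costs almost nothing.

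**What to change.** Amend section 6.iii.8 as follows.

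1. Confirm the addressee in 6.iii.8.g and replace it with *the FDA office or division responsible for this IND*. That wording is safe whichever office it proves to be.
2. Reconcile 6.iii.8.g with Table 6.iii.2 so that both name the same reactions, the same FDA and IRB clocks and the same distribution. The sponsor should state which scope was intended. If 6.iii.8.g is brought up to the table, no FDA or IRB duty is added beyond what the table already imposes.
3. State how AERS in 6.iii.8 and Form 3500A in 6.iii.8.g relate.
4. In 6.iii.8.e, cite Table 6.iii.2 in place of Table 6.iii.1. In Table 6.iii.2, replace the reference to 6.iii.8.7 with the current subsection letter.

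The cost is a wording amendment with no new study procedures. If the wider scope is adopted for distribution, slightly more reports may be circulated to investigators.
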